8.3.4.2 Regulatory Reporting Requirements for Serious Adverse Events

If a subject is permanently withdrawn from protocol required therapies because of a serious adverse event, this information must be submitted to Amgen, or its designee.

Prompt notification by the investigator to the sponsor (or designee) of serious adverse events is essential so that legal obligations and ethical responsibilities towards the safety of subjects and the safety of a study treatment under clinical investigation are met.

The sponsor (or designee) has a legal responsibility to notify both the local regulatory authority and other regulatory agencies about the safety of a study treatment under clinical investigation. The sponsor (or designee) will comply with country-specific regulatory requirements relating to safety reporting to the regulatory authority, IRBs/IECs, and investigators.

Individual safety reports must be prepared for suspected unexpected serious adverse reactions according to local regulatory requirements and sponsor (or designee) policy and forwarded to investigators as necessary.

An investigator who receives an individual safety report describing a serious adverse event or other specific safety information (eg, summary or listing of serious adverse events) from the sponsor (or designee) will file it along with the Investigator's Brochure and will notify the IRB/IEC, if appropriate according to local requirements.

To comply with worldwide reporting regulations for serious adverse events, the treatment assignment of subjects who develop serious, unexpected, and related adverse events may be unblinded by Amgen or designee before submission to regulatory authorities. Aggregate analyses may also be unblinded by the Safety Assessment Team, as appropriate. Investigators will receive notification of related serious adverse events reports sent to regulatory authorities in accordance with local requirements.

8.3.4.3 Reporting of Serious Adverse Event After the Protocol Required Reporting Period

There is no requirement to monitor study subjects for serious adverse events following the protocol required reporting period or after the EOS. However, these serious adverse events can be reported to Amgen. Per local requirements in some countries, investigators are required to report serious adverse events that they become aware of after the EOS. If serious adverse events are reported, the investigator is to report them to Amgen within 24 hours following the investigator's knowledge of the event.

Serious adverse events reported outside of the protocol-required reporting period will be captured within the safety database as clinical study cases and handled accordingly based on relationship to investigational product.

8.3.4.4 Method of Detecting Adverse Events and Serious Adverse Events

Care will be taken not to introduce bias when detecting adverse events and/or serious adverse events. Open-ended and nonleading verbal questioning of the subject is the preferred method to inquire about adverse event occurrence.

8.3.4.5 Adverse Event and Serious Adverse Event Follow-up

During the study the adverse events and serious adverse events should be followed proactively by the investigator at subsequent visits/contact. All adverse events and serious adverse events

will be followed until resolution, stabilization, until the event is otherwise explained, or until the subject is lost to follow-up. At the time the subject's study participation ends, all ongoing adverse events and serious adverse events should be evaluated for resolution. All new or updated information for previously reported serious adverse events must be sent to Amgen within 24 hours following knowledge of the new information and will be recorded in the originally completed Adverse Event CRF. If specifically requested, the investigator may need to provide additional follow-up information, such as discharge summaries, medical records, or extracts from the medical records. Information provided about the serious adverse event must be consistent with that recorded on the Adverse Event CRF.

The investigator is obligated to perform or arrange for the conduct of supplemental measurements and/or evaluations as medically indicated or as requested by Amgen to elucidate the nature and/or causality of the adverse event and serious adverse event as fully as possible. This may include additional laboratory tests or investigations, histopathological examinations, or consultation with other health care professionals.

If a subject is permanently withdrawn from protocol required therapies because of a serious adverse event, this information must be submitted to Amgen. If a subject dies during participation in the study, the investigator will provide Amgen with a copy of any post-mortem findings including histopathology if available.

Events of interest are described in Section 8.3.6. Formal pre-specified evaluations for events of interest are not planned at this time.

8.3.5 Pregnancy

Details of all pregnancies and/or lactation in female subjects and female partners of male subjects that occur after the start of study treatment and until 5 months after the last investigational product injection will be documented.

If a pregnancy is reported, the investigator is to inform Amgen and/or designee within 24 hours of learning of the pregnancy and/or lactation and is to follow the procedures outlined in Section 10.2, Appendix 2. Amgen Global Patient Safety or its designee will follow-up with the investigator regarding additional information that may be requested.

Abnormal pregnancy outcomes (eg, spontaneous abortion, fetal death, stillbirth, congenital anomalies, ectopic pregnancy) are considered serious adverse events.

Final 1.0 Date: 03 Jun 2021 Page **57** of **87**

Further details regarding pregnancy and lactation are provided in Section 10.2, Appendix 2.

8.3.6 Events of Interest

Events of interest for ABP 501/adalimumab will be defined in the Statistical Analysis Plan (SAP) and will be reviewed on an ongoing basis as part of this study. There are no additional expedited reporting requirements for events of interest, beyond what is defined for any adverse event report that qualifies to be expedited as part of regulatory reporting rules for investigational product.

8.4 Treatment of Overdose

The effects of overdose of ABP 501 are not known. Doses up to 10 mg/kg of adalimumab (15 times the recommended dose) have been administered to patients in clinical trials without evidence of dose-limiting toxicities.

8.5 Pharmacokinetics

Serum samples will be collected for measurement of serum concentrations of investigational product as specified in the Schedule of Assessments (Table 1-1). Instructions for the collection, handling, storage and shipment of biological samples will be provided in the Laboratory Manual. Blood samples for PK testing will be collected from all subjects. PK samples for baseline, week 6, week 12, week 16, week 20, and week 28 should be taken prior to administration of investigational product. PK samples for subsequent time points should be collected within the tolerance window specified in Table 1-2.

The actual date and time (24-hour clock time) of each sample will be recorded.

Samples collected for analyses of investigational product serum concentration may also be used to evaluate safety or efficacy aspects that address concerns arising during or after the study.

8.6 Pharmacodynamics

Pharmacodynamic parameters are not evaluated in this study.

8.7 Genetics

Genetics are not evaluated in this study.

Clinical Study Protocol: 20200497

Final 1.0 Date: 03 Jun 2021 Page **58** of **87**

8.8 Biomarkers

Biomarkers are not evaluated in this study.

8.9 Immunogenicity Assessments

Antibodies (binding and neutralizing) to investigational product will be evaluated in serum samples collected from all subjects. Additionally, serum samples should also be collected at the final visit from subjects who discontinued investigational product or were withdrawn from the study. These samples will be tested by the sponsor or sponsor's designee. Samples should be taken prior to administration of investigational product (predose) on dosing visits. Samples tested positive for binding antibodies may be further assessed for neutralizing antibodies. Additional blood samples may be obtained to rule out ADAs during the study.

The detection and characterization of ADAs will be performed using a validated assay method by the sponsor or under the supervision of the sponsor.

9 Statistical Considerations

9.1 General Considerations

All personnel involved with the analysis of the study will remain blinded until database lock. Analysis will be performed using SAS® version 9.4 or higher (SAS Institute, Cary, NC, US) by the sponsor or its representatives.

The SAP will be developed and finalized prior to the unblinding for the final analysis. The SAP will provide a detailed description of the statistical methods and expand on the details provided in the protocol.

Data during the lead-in period, where all subjects are receiving adalimumab, will be presented as one group for the subjects who have been treated with IP. All data post randomization will be presented by treatment group (switching group versus continued-use group). Descriptive statistics (number of observations, mean, standard deviation, median, minimum, and maximum) will be provided for continuous variable, and counts and percentages will be presented for categorical variables. Confidence intervals (CIs) and other inferential statistics may also be provided.

In general, baseline will be defined as the last non missing measurement/procedure before or on the date of first administration of investigational product.

9.2 Statistical Hypotheses

The analysis of the primary PK endpoints will test the following hypotheses for each endpoint:

Null Hypothesis (H₀): The geometric mean ratio (GMR) between ABP 501 and adalimumab is outside a prespecified margin of 0.8, 1.25,

versus

Alternative Hypothesis (H_A): The GMR between ABP 501 and adalimumab is within a prespecified margin of 0.8, 1.25.

To establish that the risk in terms of safety or diminished efficacy of switching between ABP 501 and adalimumab is not greater than the risk of using adalimumab without such switching (continuously), both of the 90% CI of GMRs of ABP 501 versus adalimumab for area under the

Final 1.0 Date: 03 Jun 2021 Page **60** of **87**

curve from time 0 over the dosing interval (AUC $_{tau}$) and C_{max} from the primary analysis must fall within the prespecified margin mentioned above.

9.3 Sample Size Determination

Approximately 414 subjects will be enrolled to receive adalimumab during the lead-in period. Subjects with prior biologic use for psoriasis will be capped at 50% of the total enrolled subjects. This sample size will ensure approximately 342 subjects will be randomized at week 12 after the lead-in period, considering 17% lead-in failures in a 1:1 ratio to the continued-use group or the switching group. The randomization will be stratified by prior biologic use for psoriasis at baseline (week 1/day 1, yes vs. no) and geographic region. The number of subjects enrolled may be adjusted during the study with the actual lead-in failure rate seen to ensure approximately 342 subjects will be randomized at week 12. Subjects already enrolled will be allowed to be randomized at week 12. The sample size of 342 randomized subjects will provide at least 90% power to demonstrate similarity of the primary PK endpoints based on the Two One-Sided Tests at a 0.05 significance level, assuming a between-subject variability (as measured by coefficient of variation) of 53% for ABP 501 and adalimumab, a true GMR of 1 between ABP 501 and adalimumab, a similarity margin of 0.8, 1.25, and 15% dropouts after randomization through week 30 (including subjects who discontinue the study prior to week 28 and those reaching week 28 but do not have evaluable primary PK endpoints between weeks 28 and 30).

9.4 Populations for Analysis

For purposes of analysis, the following analysis sets are defined in Table 9-1. The Full Analysis Set will be analyzed according to the treatment that the subject is randomized to (regardless of actual treatment received). For all other parameter sets, subjects will be analyzed according to the investigational product they actually received. A precise definition of "as actually received" will be added in the SAP.

Clinical Study Protocol: 20200497

Final 1.0 Date: 03 Jun 2021 Page **61** of **87**

Table 9-1. Populations for Analysis

Population (Analysis Set)	Description	
Lead-in Treated Set	The Lead-in Treated Set consists of all enrolled subjects treated with at least 1 dose of investigational drug during the lead-in period.	
Full Analysis Set	The Full Analysis Set consists of all randomized subjects (randomization occurs at week 12).	
Safety Analysis Set	The Safety Analysis Set consists of all randomized subjects who received at least 1 dose of investigational product post randomization.	
PK Concentration Analysis Set	The PK Concentration Analysis Set which will include all randomized subjects who received at least 1 dose of investigational product post randomization and have at least 1 reported serum concentration of ABP 501 or adalimumab.	
PK Parameter Analysis Set	The PK Parameter Analysis Set consists of all subjects who are randomized and received all assigned doses post-randomization and who have an evaluable ABP 501 or adalimumab serum concentration-time profile between weeks 28 and 30	
Per Protocol PK Parameter Analysis Set	The Per Protocol PK Parameter Analysis Set consists of all subjects in the PK Parameter Analysis Set who do not have an important protocol deviation that could affect the primary PK endpoints.	
Per Protocol Efficacy Analysis Set	The Per Protocol Efficacy Analysis Set will include all subjects who are randomized and received all assigned doses post-randomization and who have not experienced an important protocol deviation that may affect the evaluation of the efficacy endpoints.	

PASI = Psoriasis Area and Severity Index; PK = pharmacokinetic(s); SAP = statistical analysis plan.

9.5 Planned Analyses

9.5.1 Primary Endpoints

9.5.1.1 Primary Pharmacokinetic Endpoints

The primary analysis of the primary PK endpoints, AUC_{tau} , and C_{max} , between weeks 28 and 30 will be performed based on the PK Parameter Analysis Set, according to the actual treatment groups (switching group versus continued-use group).

The point estimates and 90% CIs for the GMRs between ABP 501 and adalimumab for AUC_{tau} and C_{max} between weeks 28 and 30 will be estimated using an analysis of covariance (ANCOVA) model adjusting for stratification factors, weight, and PK trough concentration at the end of the lead-in period (week 12). Prior to statistical modeling, the PK parameters will be logarithmically transformed (natural log). Point estimates and 90% CIs for the mean difference in logarithmic PK parameters will be estimated from the ANCOVA model, which will then be transformed back to the original scale to obtain the point estimates and 90% CIs for GMR.

 AUC_{tau} and C_{max} of ABP 501 and adalimumab between weeks 28 and 30 will be listed by subject and summarized descriptively by treatment group. A sensitivity analysis of the primary PK endpoints will be conducted on the Per Protocol PK Parameter Analysis Set. To establish the

risk in terms of safety or diminished efficacy of switching between ABP 501 and adalimumab is not greater than the risk of using adalimumab without such switch, the 90% CI of GMRs of ABP 501 versus adalimumab for AUC $_{tau}$ and C_{max} from the primary analysis should fall within the pre-specified similarity margin.

9.5.2 Secondary Endpoint(s)

9.5.2.1 Secondary Pharmacokinetic Endpoints

The analyses of the secondary PK endpoints of time of maximum concentration (t_{max}) between weeks 28 and 30 and trough concentration (C_{trough}) between weeks 14 and 28 will be based on the PK Parameter Analysis Set according to the actual treatment groups (switching group versus continued-use group). t_{max} will be summarized descriptively by treatment group and C_{trough} between weeks 14 and 28 will be summarized descriptively by visit and treatment group. The point estimates and 90% CIs for GMR for C_{trough} between the two treatment groups will be estimated using an ANCOVA model adjusting for stratification factors, weight, and PK trough concentration at the end of the lead-in period (week 12).

Mean serum concentration-time data post randomization will be presented graphically using PK Concentration Analysis Set.

9.5.2.2 Secondary Efficacy Endpoints

The analysis of the secondary efficacy endpoints will be based on the Per Protocol Efficacy Analysis Set according to the actual treatment groups (switching group versus continued-use group). The point estimate and 90% CI of the mean difference in PASI percent improvement from day 1 at week 30 will be estimated from an ANCOVA model adjusting for the baseline PASI value and the stratification factors. The point estimate and 90% CI of the risk differences in PASI 75, PASI 90, and PASI 100 response rates at week 30 will be estimated from a generalized linear model with an identity link adjusting for the stratification factors.

Missing data will be imputed by last observation carry forward method for PASI percent improvement from day 1 at week 30 and by non-responder imputation for PASI 75, PASI 90, and PASI 100 response rates at week 30. In addition, the PASI percent improvement from day 1 at week 30 and the PASI 75, PASI 90, and PASI 100 response rates at week 30 will be summarized descriptively by treatment group.

Clinical Study Protocol: 20200497

Final 1.0 Date: 03 Jun 2021 Page **63** of **87**

A sensitivity analysis will be conducted using observed data based on the Full Analysis Set according to randomized treatment groups.

9.5.3 Safety Endpoints

All reported adverse events will be categorized by system organ class and preferred term according to the Medical Dictionary for Regulatory Activities (latest version at the time of final analysis) dictionary and graded by CTCAE, version 4.03.

Safety analyses of the safety endpoints will be performed based on the Safety Analysis Set according to the actual treatment groups (switching group versus continued-use group). Treatment-emergent adverse events post randomization are defined as adverse events that start or worsen on or after the first dose of investigational product post randomization and prior to the EOS. The numbers and percentages of subjects reporting treatment-emergent adverse events, serious adverse events and events of interests will be tabulated by treatment group. The number and percent of subjects developing binding or neutralizing antidrug antibody (ADA) in the subset of Safety Analysis Set who have at least one ADA result post randomization will be tabulated descriptively by treatment group and by visit.

Laboratory data (hematology, serum chemistry, and urinalysis) will be converted to Système International units for reporting purposes. Absolute values and changes from week 12 for laboratory data post randomization will be summarized descriptively by treatment group and visit.

For vital signs post randomization, absolute values, and changes from week 12 will be summarized descriptively by treatment group and visit.

Physical examination values post randomization will be summarized descriptively by treatment group and by visit.

9.5.4 Other Analyses

9.5.4.1 **Efficacy**

The analyses of the other efficacy endpoints in this section will be based on the Per Protocol Efficacy Analysis Set.

Clinical Study Protocol: 20200497

Final 1.0 Date: 03 Jun 2021 Page **64** of **87**

The PASI percent improvement from day 1 at other time points between week 12 and week 30 and the PASI 75, PASI 90, and PASI 100 response rates at other time points between week 12 and week 30 will be summarized descriptively by treatment group.

Body surface area absolute values and changes from baseline will be summarized descriptively by visit and actual treatment group; the change from baseline in BSA at week 30 will be analyzed in a similar manner as the PASI percent improvement from baseline at week 30.

The sPGA scores will be summarized descriptively by visit and treatment group. The sPGA response (0/1) will also be summarized descriptively by visit and actual treatment group; the sPGA response (0/1) at week 30 will be analyzed similarly as the PASI 75 and PASI 100 response rates at week 30.

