4.1 Overall Design

This is a randomized, double-blind, phase 3 study in adult subjects with moderate to severe Ps. This study is planned to be conducted globally at study centers including but not limited to North America and Europe.

The total duration of study participation for each subject will be about 36 weeks, with up to 4 weeks for screening and approximately 32 weeks after the first investigational product administration.

Table 4-1. Investigational Product Groups

Reference Group Adalimumab Continued-use Group	Continued-use of adalimumab administered by SC injection using prefilled syringes at a dose of mg (2 x mg loading dose) on week 1/day 1 and mg administered 1 week later at week 2/day 8, then at 2 weeks interval at week 4, week 6, week 8, and week 10. Subsequent dosing will be at mg every 2 weeks thereafter up to and including week 28.	
Test Group Switching Group	Switching group with adalimumab administered by SC injection using prefilled syringes at a dose of mg (2 x mg loading dose) on week 1/day 1 and mg administered 1 week later at week 2/day 8, then at 2 weeks interval at week 4, week 6, week 8, and week 10. • At week 12, subjects will be switched to ABP 501 and administered ABP 501 mg SC on weeks 12 and 14. • At week 16, subjects will be switched back to adalimumab and administered adalimumab mg SC on weeks 16 and 18. • At week 20, subjects will then be switched to ABP 501 and administered ABP 501 mg SC on weeks 20, 22, 24, 26, and with last dose on	

SC = subcutaneous.

The study is composed of two periods. A lead-in period of treatment with adalimumab (weeks: 1 to 12) followed by a randomized two parallel arm period (weeks: 12 to 32). Subjects will receive an initial 6 doses of adalimumab on day 1/week 1 (mg loading dose), 1 week later on day 8/week 2 (mg), then at 2 weeks interval on week 4, week 6, week 8, and week 10 (mg), administered subcutaneously (SC). At week 12, subjects with Psoriasis Area and Severity Index (PASI) ≥ 50 (PASI 50) response will be randomized to either the continued-use group or switching group in a 1:1 ratio, stratified by geographic region and prior biologic use at baseline (week 1/day 1, yes vs. no). Subjects achieving less than PASI 50 response at week 12 visit will be considered non-responders and will be discontinued from the study at week 12. These subjects will be asked to complete End of Study (EOS) Visit procedures. Subjects randomized to the continued-use group will continue on adalimumab

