6.5 Per-protocol Efficacy Analyses Set

The Per-protocol Efficacy Analysis Set consists of all subjects who are randomized and receive all assigned doses post-randomization and who have not experienced an important protocol deviation that may affect the evaluation of the efficacy endpoints. This analysis set will be used for primary analysis of the secondary efficacy endpoints and will be analyzed according to actual treatment received.

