9.6.2.2 Secondary Analyses

These endpoints will also be summarized descriptively by actual treatment group based on Per-protocol Efficacy Analysis Set using observed data.

Sensitivity analyses will be conducted by repeating the models in section 9.6.2.1 using observed data in the FAS according to randomized treatment groups and in the Perprotocol Efficacy Analysis Set according to the actual treatment groups.

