9.6.3 Analyses of Other Efficacy Endpoint(s)

The analyses of the other efficacy endpoints in this section will be based on the Perprotocol Efficacy Analysis Set by actual treatment group.

The PASI percent improvement from day 1 at weeks 6, 12, 16 and 20 and the PASI 75, PASI 90 and PASI 100 response rates at weeks 6, 12,16 and 20 will be summarized descriptively by treatment group based on observed data.

BSA absolute values and changes from baseline will be summarized descriptively by visit (at weeks 6, 12, 16, 20 and 30) and treatment group using observed data. In addition, the point estimate and 90% CI of the mean difference in the change from baseline for BSA at Week 30 between the two groups will be estimated from an ANCOVA model adjusting for the baseline BSA value and the stratification factors with missing values imputed by LOCF.

sPGA scores will be summarized descriptively by visit (at weeks 6, 12, 16, 20 and 30) and treatment group. sPGA response (0/1) will also be summarized descriptively by visit and treatment group using observed data. The sPGA response (0/1) at Week 30 will be analyzed by a generalized linear model adjusting for the stratification factors with missing values imputed by NRI. Confidence interval for response rate will be calculated by the Clopper-Pearson method.

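### The week 16 and week 20 efficacy summaries use only subjects who later received every dose to week 28; add the same summaries for all randomized subjects.

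*Protocol*

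**What the plan says.** **Endpoints and visits.** Protocol 9.5.4.1 covers "The PASI percent improvement from day 1 at other time points between week 12 and week 30", the PASI 75/90/100 response rates at the same time points, and BSA and sPGA by visit. It opens with "The analyses of the other efficacy endpoints in this section will be based on the Per Protocol Efficacy Analysis Set". SAP 9.6.3 keeps that set and names the visits: "The PASI percent improvement from day 1 at weeks 6, 12, 16 and 20", with the response rates at those visits. Its BSA and sPGA summaries cover weeks 6, 12, 16, 20 and 30. The PASI and BSA by-visit summaries and the sPGA response are on observed data.

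**Analysis set.** SAP 6.5 limits the Per-protocol Efficacy set to subjects who are "randomized and receive all assigned doses post-randomization and who have not experienced an important protocol deviation" of a kind that may affect the efficacy evaluation. Protocol 9.4 has the same two conditions.

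**Full Analysis Set.** SAP 9.6.2.2 says "Sensitivity analyses will be conducted by repeating the models in section" 9.6.2.1, using observed data by randomized group in the Full Analysis Set. The models in 9.6.2.1 are for week 30 only. The matching sentence in protocol 9.5.2.2 also belongs to the week 30 secondary endpoints.

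**The concern.** In the switching group, week 16 follows the first block of ABP 501 (doses at weeks 12 and 14), and week 20 follows the return to adalimumab (doses at weeks 16 and 18). They are the only scheduled efficacy visits between the week 12 randomization visit and week 30. Whether a subject's week 16 score appears in the table depends on dosing that happens after the score was taken.

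Protocol 4.2 gives as the purpose of the study to show that switching carries no greater risk of diminished efficacy. Early loss of response after a switch is one form that diminished efficacy could take. Subjects who lose response and stop are the ones these tables cannot show. At stake is how complete the descriptive evidence is at two visits. No test or decision rule uses these tables.

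**Working it through.** No stated figure of the plan is in dispute. The check is a trace, followed by the little arithmetic that applies.

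**1. Doses that decide membership.** Protocol 4.1 places post-randomization doses at weeks 12, 14, 16, 18, 20, 22, 24, 26 and 28, which is nine doses. Predose week 16 scores are filtered on doses up to 28 − 16 = 12 weeks later, and week 20 scores on doses up to 28 − 20 = 8 weeks later. Missing one of the nine doses for any reason removes the subject from every visit.

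**2. Are the scores collected?** Yes. The Schedule of Assessments (Table 1-1) marks PASI/sPGA/BSA at weeks 16 and 20. Protocol 7.1 also recommends keeping subjects who stop product in the study, partly for efficacy data.

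**3. Does another planned efficacy analysis use them?**

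| Analysis | Set | Visit | Uses the week 16 or 20 score of a subject who stops early? |
|---|---|---|---|
| SAP 9.6.3 by-visit summaries | Per-protocol Efficacy | 6, 12, 16, 20, 30 | No, outside the set |
| SAP 9.6.2.1 models (LOCF, NRI) | Per-protocol Efficacy | 30 | No; LOCF works only inside the set |
| SAP 9.6.2.2 sensitivity, Full Analysis Set | All randomized | 30, observed data | No; week 30 values only |
| SAP 9.6.2.2 sensitivity, Per-protocol | Per-protocol Efficacy | 30, observed data | No, outside the set |

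The End of Study column of Table 1-1 has no PASI/sPGA/BSA mark, so a subject who leaves early may have no week 30 value either. For that subject, the week 16 and 20 scores enter no planned efficacy summary. SAP 6.1 says in general terms that the Full Analysis Set serves efficacy sensitivity analyses, but no section applies it at week 16 or 20.

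**4. Rough number excluded.** Protocol 9.3 assumes 15% loss after randomization: 342 × 0.15 = 51.3, about 51 subjects or 26 per arm. This is a proxy only. It includes subjects who reach week 28 but lack evaluable PK, some of whom may belong to the efficacy set. It is also not built to count everyone with a missed dose or an efficacy-related deviation.

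**5. When the displayed difference shifts.** Let p be the response rate in the Per-protocol set (taken as equal in both arms), q the rate among the excluded (also equal), and f the fraction excluded. Then

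all-randomized difference (switching − continued) = (f_continued − f_switching) × (p − q),

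while the Per-protocol table shows 0. With assumed values p = 80% and q = 25%:
- f = 15% in both arms: 0 × 55 = 0 points
- f = 15% switching, 10% continued: −5% × 55 = −2.75 points
- f = 20% switching, 10% continued: −10% × 55 = −5.5 points

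With q = p, the shift is zero at any f. These inputs are not in the documents. The example shows only which conditions are needed.

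**The case against.** The strongest reply is that these are descriptive summaries of other endpoints. All listed efficacy endpoints are at week 30, and the interchangeability conclusion rests on the AUCtau and Cmax intervals (protocol 9.2, SAP 2.2). That stands. A reader might infer that the selection undermines the interchangeability conclusion or the week 30 models. The documents do not support this, because neither uses these tables.

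Second, other outputs limit the harm. SAP 9.2 summarizes discontinuations and exclusions from each set with reasons, so unequal removal would be visible. Protocol 8.3.1.1.1 does not count lack of efficacy in itself as an adverse event, but exacerbations and clinical consequences that meet the definition are reported, and SAP 9.7.1 tabulates events leading to discontinuation. Trough concentrations (SAP 9.5.2, PK Concentration set) and antidrug antibodies (SAP 9.7.6, Safety Analysis Set) are shown by visit in sets without the all-doses condition. This also stands, though none of it replaces the PASI, sPGA and BSA scores.

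Third, using one set for the by-visit and week 30 results gives a coherent profile. That is a reason to keep the Per-protocol tables, not a reason to omit the others.

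A reader might also want a firmer size. Combining the 15% loss with an assumed 1% to 3% miss rate per dose gives 342 × 0.85 × 0.99^9 = 266 down to 342 × 0.85 × 0.97^9 = 221 subjects retained. The miss rates have no source, and the product may count the same subjects twice, since the 15% may already include some who missed doses. Similarly, a true 10-point loss can be made to display as about 4.5 points, but only by assuming that 80% of switch-related failures leave the set. If 30% leave, the same model displays about 9 points. (Both assume 75% response under continued use, with 88% of responders and 70% of ordinary non-responders retained.) The documents give no reason to prefer the first. The PASI 50 stopping rule applies only at week 12, and later withdrawal for alternative therapy is discretionary (protocol 7.2).

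**Conclusion.** The point holds as a limited, inexpensive improvement. The plan conditions the week 16 and 20 efficacy summaries on later dosing and deviations. For a subject who leaves early, it uses the collected scores in no efficacy summary.

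It would be too strong to say that the tables do draw the groups together. They could understate an early difference only if exclusion is related to loss of response and operates differently in the two groups. Exclusion unrelated to outcome produces no systematic shift, and neither does equal exclusion of subjects with similar response. The size of any understatement cannot be derived from the documents. The figure of about 51 of 342 indicates only the rough scale of possible exclusion.

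The sponsor has already acted on a related argument: SAP section 10 removes the all-doses condition from the PK Parameter set because it could exclude evaluable subjects. The efficacy set keeps that condition.

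**What to change.** In SAP 9.6.3 and protocol 9.5.4.1, add observed-data summaries of PASI percent improvement, PASI 75/90/100, sPGA (score and 0/1 response) and BSA at weeks 16 and 20 for the Full Analysis Set by randomized group. Show the number of subjects contributing at each visit in each group. Keep the Per-protocol tables as supportive. If the protocol is not amended, record the addition in SAP section 10.

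The cost is a few extra tables from existing programs run on another set. No new visits, data or subjects are needed, and sample size, error rate and power are unchanged.
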